8.9.2 Pharmacodynamic Analysis

CCI

CCI

8.10 Other Outcomes

Not applicable.

8.11 Safety Analysis

Safety analyses include AEs, clinical laboratory parameters, vital sign parameters, 12-lead ECG results, and other safety parameters. The Safety Set will be used for all summaries of safety parameters. The safety endpoints will be presented by pooled placebo, each TAK-831 dose level, TAK-831 overall, and overall.

8.11.1 Adverse Events

A pretreatment event (PTE) is defined as any untoward medical occurrence in a clinical investigation subject who has signed informed consent to participate in a study, but prior to administration of any study medication; it does not necessarily have to have a causal relationship with study participation.

An AE is defined as any untoward medical occurrence in a clinical investigation subject administered a drug; it does not necessarily have to have a causal relationship with this treatment. PTE and AE verbatim terms will be coded by SOC and PT using MedDRA (version 20.0 or later).

TEAEs will be defined as any sign, symptom, syndrome, or new illness, regardless of relationship to study drug, that occur after the first dose of study drug and up to 30 days (onset date – last date of dose + 1 ≤ 30) after the last dose of study drug or early termination.

TEAEs are recorded in the eCRF as being related or not related to study drug and study procedure. TEAEs that are recorded as related to study drug and/or study procedure will be summarized separately. TEAEs will also be presented by intensity/severity (mild, moderate, and severe). Serious TEAEs, TEAEs leading to study drug discontinuation, and TEAEs leading to death will also be summarized using SOC and PT.

When calculating the frequency and percentage of subjects who reported TEAEs, a subject will be counted only once for each SOC or PT when multiple TEAEs are coded to the same SOC or PT. For the intensity or relatedness summaries, if a subject reports multiple TEAEs coded to the same SOC or PT, the TEAE with maximum intensity or strongest relationship will be included in the summary.

AEs with missing intensity will be listed as such in the AE listings, however, will be summarized as severe in summary tables. If the relationship of an event is missing, the relationship for the event will be considered to have been related.

In general, AEs will be tabulated at the following levels: overall summary (subjects with at least 1 AE in any dose or regimen), the MedDRA SOC, and the MedDRA PT. The tables will include the number and percentage (N[%]) of subjects. The following summary tables will be generated for each study part:

- Overview of Treatment-Emergent Adverse Events.
- Treatment-Emergent Adverse Events by System Organ Class and Preferred Term.
- Treatment-Emergent Adverse Events by Preferred Term.

- Serious Treatment-Emergent Adverse Events by System Organ Class and Preferred Term.
- Relationship of Treatment-Emergent Adverse Events to Study Drug by System Organ Class and Preferred Term.
- Drug-Related Treatment-Emergent Adverse Events by System Organ Class and Preferred Term.
- Drug-Related Treatment-Emergent Adverse Events by Preferred Term.
- Intensity of Treatment-Emergent Adverse Events by System Organ Class and Preferred Term.
- Pretreatment Adverse Events by System Organ Class and Preferred Term.

In addition, subject mappings for the TEAEs by SOC and PT will be generated.

Data listings will be provided for PTEs, TEAEs, TEAEs leading to study drug discontinuation, liver function abnormalities, SAEs, and AEs that resulted in death. AEs happened after 30 days post the last dose of the study drug will be listed as well.

8.11.2 Clinical Laboratory Evaluations

Clinical laboratory tests will be assessed using the Safety Set and will be evaluated and presented using International System of Units (SI) units unless otherwise stated. Refer to Protocol Section 9.2.9.1 and 9.2.9.2 as well as the schedule of the events for a list of all clinical laboratory tests.

All laboratory test parameters will be displayed in individual subject data listings in both SI units and conventional (CV) units. For test results not in SI units, the conversion to SI units will be done in the derived SDTM and ADaM datasets using the known conversion factors. If necessary, SI units from the central laboratory may be converted to Takeda's preferred SI units in the derived SDTM and ADaM datasets. All summaries and analyses will be based on the values using these preferred SI units.

Only observations within 7 days of the last dose of study drug will be included in the tables. No inferential statistics will be presented unless otherwise stated.

Descriptive statistics (N, mean, SD, median, minimum, and maximum) for the observed and change from baseline values will be presented. Study baseline will be used for change from baseline. Note that "character" urinalysis tests will only be listed.

Laboratory MAVs, identified by the criteria defined in [Appendix A](#), will be tabulated. If a subject has a MAV for a particular laboratory test, all visits for that subject for that parameter will be listed. The number and percentage of subjects with at least 1 postdose markedly abnormal laboratory test result will be summarized. The mapping of the subjects who meet the MAV criteria will be listed as a table. All observations, including ones at unscheduled visits, will be included in the MAV evaluation and summaries.

Listings of all clinical safety laboratory data will be provided in Appendix 16.2 and will be presented in both SI and CV units. Laboratory data outside of the normal reference range will be

indicated in the listings. In addition, MAVs will be flagged. The listing will include site number, subject identifier, age, gender, treatment group, study visit, and sample collection date.

8.11.3 Vital Signs

Descriptive statistics (N, mean, SD, median, minimum, and maximum) will be used to summarize vital sign parameters at baseline, each post-baseline visit, and change from baseline to each post-baseline visit. Only observations within 7 days of the study drug will be included in the tables.

Vital sign MAVs, identified by the criteria defined in [Appendix B](#), will be tabulated. If a subject has a MAV for a particular vital signs parameter, all visits for that subject for that parameter will be listed. The number and percentage of subjects with at least 1 postdose markedly abnormal vital signs measurement will be summarized. The mapping of the subjects who meet the MAV criteria will be listed as a table. All observations, including ones at unscheduled visits, will be included in the MAV evaluation and summaries.

Orthostatic hypotension, identified by the criteria defined in [Appendix C](#), will be calculated at every time point where standing and supine measurements are available using the formula: standing vital measurement – supine vital measurement. The mapping of the subjects who meet the criteria for orthostatic hypotension will be listed by study visit as a table. All orthostatic hypotension observations, including ones at unscheduled visits, will be included in the subject mappings.

Listings of all vital signs data will be provided in Appendix 16.2. Vital sign MAVs will be flagged in the listings. The listing will include site number, subject identifier, age, gender, treatment group, study visit, and sample collection date.

8.11.4 12-Lead ECGs

Descriptive statistics (N, mean, SD, median, minimum, and maximum) of ECG parameters, including heart rate, PR interval, RR interval, QRS interval, QT interval, and QTc interval (Fredericia's and Bazett's corrections), will be presented for baseline, each post-baseline visit, and change from baseline to each post-baseline visit. Only the scheduled measurements will be included in the summary. Only observations within 7 days of the study drug will be included in the tables. No inferential statistics will be presented.

ECG MAVs, identified by the criteria defined in [Appendix D](#), will be tabulated. If a subject has a MAV for a particular 12-lead ECG parameter, all visits for that subject for that parameter will be listed. The number and percentage of subjects with at least 1 postdose markedly abnormal 12-lead ECG measurement will be summarized. The mapping of the subjects who meet the MAV criteria will be listed as a table. All observations, including ones at unscheduled visits, will be included in the MAV evaluation and summaries.

Overall ECG interpretation category (normal, abnormal not clinically significant, abnormal clinically significant) is collected by eCRF at baseline and at each scheduled post-baseline visit. Shifts in ECG interpretation will be presented as cross-tabulations (baseline versus each post-

baseline visit) of numbers of subjects with normal, abnormal not clinically significant, and abnormal clinically significant interpretations with missing, if applicable, and total categories by regimen.

Listings of all 12-lead ECG data will be provided in Appendix 16.2. MAVs will be flagged in the listings. The listing will include site number, subject identifier, age, gender, treatment group, study visit, and sample collection date.

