- 10. The subject has evidence of current significant cardiovascular, central nervous system, hepatic, hematopoietic disease, renal dysfunction, metabolic or endocrine dysfunction, serious allergy, asthma, hypoxemia, hypertension, seizures, or allergic skin rash. There is any finding in the subject's medical history, physical examination, or safety laboratory tests giving reasonable suspicion of a disease that would contraindicate taking TAK-831, or a similar drug in the same class, or that might interfere with the conduct of the study. This includes, but is not limited to, peptic ulcer disease, seizure disorders, and cardiac arrhythmias.
- 11. The subject has a QT interval with Fridericia's correction method (QTcF) >450 ms (male subjects) or >470 ms (female subjects) or PR outside the range of 120 to 220 ms, confirmed with 1 repeat testing, at the Screening Visit and Check-in. If repeat testing is required, QTcF and PR values should be based on the average of the assessments.
- 12. The subject has current or recent (within 6 months) gastrointestinal disease that would be expected to influence the absorption of drugs (ie, a history of malabsorption, esophageal reflux, peptic ulcer disease, erosive esophagitis, frequent [more than once per week] occurrence of heartburn, or any surgical intervention).
- 13. The subject has a history of cancer, except basal cell carcinoma that has been in remission for at least 5 years before first dose of study medication.
- 14. The subject has a positive test result for HBsAg, anti-HCV, or HIV antibody/antigen at Screening.
- 15. The subject has used nicotine-containing products (including but not limited to cigarettes, pipes, cigars, chewing tobacco, nicotine patch or nicotine gum) within 28 days before Check-in. Cotinine test is positive at Screening or Check-in.
- 16. The subject has poor peripheral venous access.

- 17. The subject has donated or lost 450 mL or more of his or her blood volume (including plasmapheresis), or had a transfusion of any blood product within 45 days before the first dose of study medication.
- 18. The subject has a Screening or Check-in abnormal (clinically significant) ECG. Entry of any subject with an abnormal (not clinically significant) ECG must be approved, and documented by signature by the principal investigator or designee.

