6.0 ANALYSIS ENDPOINTS

6.1 Primary Endpoints

Primary endpoints for the study include:

- Percentage of subjects who experience at least 1 treatment emergent adverse event (TEAE).
- Percentage of subjects who meet the markedly abnormal criteria for clinical safety laboratory tests at least once postdose.
- Percentage of subjects who meet the markedly abnormal criteria for vital sign measurements at least once post dose.
- Percentage of subjects who meet the markedly abnormal criteria for 12-lead safety electrocardiogram (ECG) parameters at least once post dose.

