Appendix D Criteria for Out-of-Range Values for the 12-Lead ECG Parameters

Parameter	Lower Criteria	Upper Criteria
Heart rate	<50 beats per minute	>120 beats per minute
PR	≤80 milliseconds	≥200 milliseconds
QT Interval	≤300 milliseconds	≥460 milliseconds
QTcB Interval	≤300 milliseconds	≥500 milliseconds OR ≥30 milliseconds change from baseline and ≥450 milliseconds
QTcF Interval	≤300 milliseconds	≥500 milliseconds OR ≥30 milliseconds change from baseline and ≥450 milliseconds
QRS	≤80 milliseconds	≥180 milliseconds

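### Several absolute limits for markedly abnormal vital signs and ECG values can be met by eligible subjects before dosing, and the percentages for primary endpoints 3 and 4 do not separate those subjects

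*SAP*

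**What the plan says.** Primary endpoint 4 in SAP 6.1 is "Percentage of subjects who meet the markedly abnormal criteria for 12-lead safety electrocardiogram (ECG) parameters at least once post dose". Endpoint 3 is worded the same way for vital signs, and Protocol 5.2.1 matches both. For the tables, SAP 8.11.4 says "The number and percentage of subjects with at least 1 postdose markedly abnormal 12-lead ECG measurement will be summarized" and SAP 8.11.3 says "The number and percentage of subjects with at least 1 postdose markedly abnormal vital signs measurement will be summarized". Unscheduled readings count in both. Neither section conditions the count on baseline.

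In SAP Appendix D the PR row has the upper limit "≥200 milliseconds" and the heart-rate row the lower limit "<50 beats per minute". Both are absolute, as are QRS ≤80 ms and uncorrected QT ≥460 ms. Appendix B has pulse <50 bpm and body temperature <35.6 or >37.7 °C, also absolute, although its title announces changes from baseline. The only criterion that uses baseline is the second limb for QTcB and QTcF, which needs "≥30 milliseconds change from baseline" together with a value of at least 450 ms.

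At entry, Protocol 7.2 item 11 excludes subjects with "PR outside the range of 120 to 220 ms, confirmed with 1 repeat testing". Item 20 admits a resting heart rate of 40 to 100 bpm and exempts the rate read from the ECG. Item 18 excludes a clinically significant abnormal ECG but lets other abnormal ECGs enter with documented approval.

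**The concern.** A postdose abnormality count is naturally read as something that appeared after dosing. Here a subject with a steady PR of 210 ms, or a steady pulse of 46 bpm, is eligible, does not change, and is still counted, on placebo or on TAK-831. Two of the four primary endpoints therefore mix values present before dosing with values that arose afterwards. With six active subjects per cohort, the chance placement of one such subject in a dose group could be mistaken for a dose effect.

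**Working it through.** **Entry range against limit**

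| Parameter | Allowed at entry | Markedly abnormal | Eligible and already flagged |
|---|---|---|---|
| PR | 120–220 ms | ≥200 ms | 200–220 ms |
| Pulse | 40–100 bpm | <50 bpm | 40–49 bpm |
| ECG heart rate | no numeric range | <50 bpm | any value <50 that passes item 18 |
| QRS | no numeric range | ≤80 ms | any such value that passes item 18 |
| Uncorrected QT | no numeric range | ≥460 ms | any such value that passes item 18 |
| Body temperature | no numeric range | <35.6 or >37.7 °C | any such value |
| Systolic pressure | 90–140 mm Hg | <85 or >180 mm Hg | none |
| Diastolic pressure | 50–90 mm Hg | <50 or >110 mm Hg | none |

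**Weight of one subject.** Each cohort has 6 active and 2 placebo subjects. One unchanged but flagged subject is 1/6 = 16.7 points in a dose group, 1/12 = 8.3 points in pooled placebo if all six cohorts run, and 1/36 = 2.8 points in TAK-831 overall.

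**How often it could happen.** The plan gives no expected rate to reproduce and no pulse, heart-rate or PR distribution. The rest is an illustration with no drug effect.

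Inputs from the documents are the limits, the entry ranges and the scheduled postdose readings in Protocol 3.0, footnotes (f) and (i):

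- Pulse: 3 (Day 1) + 1 (Day 2) + 14 × 4 (Days 3 to 16) + 1 (exit) = 61 supine time points. Standing and unscheduled readings are left out.
- Safety ECG: 1 (Day 1) + 1 (Day 10) + 3 (Day 16) + 1 (exit) = 6.

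Assumed inputs are normal, independent readings with these values:

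- Pulse and ECG heart rate: mean 65 (60 to 70), between-subject SD 8, within-subject SD 3 or 5.
- PR: mean 160 (150 to 170), between-subject SD 18 or 22, within-subject SD 8.

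For a subject with true mean m, the chance q that one reading is flagged is Φ((50 − m)/SDw) for the rates and 1 − Φ((200 − m)/SDw) for PR. The chance of any postdose flag is 1 − (1 − q)^k, with k = 61 or 6. This is averaged over subjects, with the baseline reading inside the entry range where one exists, and divided by whether the baseline reading also met the limit. The chance of at least one flagged subject in six is 1 − (1 − p)^6, where p is the share flagged.

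| Central case (low to high SD) | Any flag | Not met at baseline | Already met at baseline | At least 1 in 6: any flag | At least 1 in 6: not met at baseline |
|---|---|---|---|---|---|
| Pulse, mean 65 | 16.0–33.9% | 12.3–28.8% | 3.7–5.1% | 65–92% | 54–87% |
| ECG heart rate, mean 65 | 8.7–15.7% | 5.2–11.3% | 3.5–4.5% | 42–64% | 27–51% |
| PR, mean 160 | 5.6–9.3% | 3.9–5.7% | 1.7–3.6% | 29–44% | 21–30% |

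Over the full range of means, the share flagged and already met at baseline is 0.9–12.8% for pulse, 0.8–12.7% for ECG heart rate and 0.4–7.8% for PR. In the central cases these subjects are 15–23% of pulse flags, 29–40% of ECG heart-rate flags and 30–38% of PR flags. Judging entry on separate Screening and Check-in readings hardly changes the result (pulse 3.6–5.0%, PR 1.6–3.4%).

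QRS can be as large. With an assumed mean of 90 to 95 ms, between-subject SD 8 to 10 and within-subject SD 4, 3.9–16.5% already meet the limit; at mean 100 it is 1.0–2.7%.

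**What a split by baseline cannot do.** Take a steady subject with true pulse 52 and within-subject SD 3. Each reading is flagged with probability 0.252, so at least one of 61 is flagged almost surely. The single baseline reading misses the limit with probability 0.748, so this unchanged subject usually falls among those not flagged at baseline.

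**The case against.** The SAP does what the protocol asks. The protocol endpoint is presence of a markedly abnormal value after dosing, not emergence; the emergent primary endpoint is the TEAE one. The study is descriptive and was not sized on power. Planned output also lets a reader trace the subjects: "If a subject has a MAV for a particular vital signs parameter, all visits for that subject for that parameter will be listed", the ECG section has the same rule, and subject mappings, change-from-baseline summaries and an ECG shift table are planned. Item 18 gives ECGs a partial gate before dosing. All of this stands. But the shift table covers the investigator's overall interpretation, not the PR or heart-rate criteria, and none of these outputs splits the percentages. Table shells are not among the documents, so the point rests on what SAP 8.11.3 and 8.11.4 specify.

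A reader might infer more than the documents support:

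- **Bias between arms.** Pooled placebo is counted by the same rule and allocation is randomized. The result is inflation and noise.
- **Distorted dose escalation.** The criteria in Protocol 6.2 rest on exposure, serious or severe events and psychiatric symptoms, not on these percentages.
- **Subjects that cannot be identified.** The listings identify them.
- **A problem of PR, pulse and ECG heart rate alone.** QRS, uncorrected QT and temperature also have absolute limits and no numeric entry range.
- **Every row affected.** The blood pressure ranges do not overlap their limits, and the second QTc limb already requires a change.

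**Conclusion.** The point holds on the text. Eligible subjects can meet several absolute limits before dosing, and the counts for endpoints 3 and 4 include them without distinction. Its size is modest: 16.7 points per such subject in a dose group of six, and about 0.4% to 13% of subjects per parameter for pulse, ECG heart rate and PR. That range rests wholly on assumed means, SDs, normality and independent readings, so confidence is high for the overlap and low for the rate. The figures are per parameter, whereas each endpoint counts a hit on any parameter; the effect on the whole endpoint was not computed. In the central cases most flags are in subjects who did not meet the limit at baseline, and for pulse the main driver is one baseline reading set against up to 61 postdose readings. The change is worth making because it is cheap and clarifies two primary percentages; it does not call the design into question.

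**What to change.** In SAP 8.11.3 and 8.11.4, keep the count as the protocol words it. In the same table, for every vital-sign and ECG parameter and by treatment, split it into (a) criterion met after dosing but not at baseline and (b) criterion already met at baseline, using the baseline defined in SAP 8.1. Show change from baseline for the subjects in (b), so that worsening from an abnormal start is not lost. Do not label (a) as drug effect, since it still holds chance flags from repeated readings. Separately, reconcile the Appendix B title with its absolute limits.

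The cost is two extra rows per parameter and a baseline flag, from data already collected. No endpoint, entry criterion or stopping rule changes. The drawback is that most flags stay, including those in subjects who enter just on the normal side of a limit.

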8.11.5 CCI

CCI

8.11.6 Other Observations Related to Safety

Follow-up phone calls, DNA sample collections, physical and neurological examination and suicidality assessments (C-SSRS) will be presented in data listings.

8.12 Interim Analysis

This is an investigator-subject blinded, sponsor unblinded study. No formal interim analysis is planned.

CCI

8.13 Changes in the Statistical Analysis Plan

Not Applicable.

Appendix A Criteria for Identification of Markedly Abnormal Laboratory Values

Hematology—Criteria for Markedly Abnormal Values

Parameter	Unit	Low Abnormal	High Abnormal
Hemoglobin	Both	< 0.8 × LLN	> 1.2 × ULN
Hematocrit	Both	< 0.8 × LLN	> 1.2 × ULN
RBC count	Both	< 0.8 × LLN	> 1.2 × ULN
WBC count	Both	<0.5 x LLN	>1.5 x ULN
Platelet count	Conventional	<75 x 10 ³ /μL	>600 x 10 ³ /μL
	SI	<75 x 10 ⁹ /L	>600 x 10 ⁹ /L

LLN=lower limit of normal, RBC=red blood cell, ULN=upper limit of normal, WBC=white blood cell.

Serum Chemistry—Criteria for Markedly Abnormal Values

Parameter	Unit	Low Abnormal	High Abnormal
ALT	Both	--	>3x ULN
AST	Both	--	>3x ULN
GGT	Both	--	>3x ULN
Alkaline phosphatase	Both	--	>3x ULN
Total bilirubin	Conventional	--	>2.0 mg/dL
	SI	--	>34.2 μmol/L
Albumin	Conventional	<2.5 g/dL	--
	SI	<25 g/L	--
Total protein	Both	<0.8x LLN	>1.2x ULN
Creatinine	Conventional	--	>2.0 mg/dL
	SI	--	>177 μmol/L
Blood urea nitrogen	Conventional	--	>30 mg/dL
	SI	--	>10.7 mmol/L
Sodium	Conventional	<130 mEq/L	>150 mEq/L
	SI	<130 mmol/L	>150 mmol/L
Potassium	Conventional	<3.0 mEq/L	>6.0 mEq/L
	SI	<3.0 mmol/L	>6.0 mmol/L
CPK	Both	--	>5x ULN
Glucose	Conventional	< 50 mg/dL	>350 mg/dL
	SI	< 2.8 mmol/L	>19.4 mmol/L

ALT=alanine aminotransferase, AST=aspartate aminotransferase, CPK=creatine phosphokinase, GGT=γ-glutamyl transferase, LLN=lower limit of normal, ULN=upper limit of normal.

Appendix B Criteria for Abnormal Changes from Baseline of Vital Signs

Parameter	Unit	Lower Criteria	Upper Criteria
Pulse	bpm	<50	>120
Systolic blood pressure	mm Hg	<85	>180
Diastolic blood pressure	mm Hg	<50	>110
Body temperature	°C	< 35.6	>37.7

Appendix C Criteria for Identification of Markedly Abnormal Orthostatic Changes

Parameter	Criteria
Orthostatic Hypotension	(Orthostatic Systolic Blood Pressure < -20 mm Hg OR Orthostatic Diastolic Blood Pressure < -10 mm Hg) AND Heart Rate Increase > 20 beats/min

Note: Orthostatic measurement = standing vital measurement – supine vital measurement.

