#### PD/BIOMARKER EVALUATIONS

CCI

CCI

AE=adverse event, anti-HCV=antibody to hepatitis C virus, BMI=body mass index, C-SSRS=Columbia–Suicide Severity Rating Scale, ECG=electrocardiogram, FSH=follicle-stimulating hormone, HbA1c=glycosylated hemoglobin, HBsAg=hepatitis B surface antigen, hCG=human chorionic gonadotropin, HIV=human immunodeficiency syndrome, PGx=pharmacogenomics, TSH=thyrotropin.

- (a) Study exit for non-CSF cohorts occurs on Day 17 and for CSF cohorts on Day 19.
- (b) At Early Termination, perform all procedures per Section 7.6.
- (c) The Follow-up Visit will occur by telephone on Day 30 (±2) unless abnormal, clinically significant findings are observed upon discharge. In these cases, subjects must be brought back to the clinic for re-evaluation per investigator's discretion. (X) is for optional procedure.
- (d) BMI will be calculated only at Screening.
- (e) Record all ongoing medications from Screening and throughout the study.
- (f) Vital signs (oral temperature, respiratory rate, pulse, and blood pressure) will be obtained at Screening, Check-in, Day 1, and Days 3 through 16 at predose (within 60 minutes before dosing) and at 1, 4, and 12 hours after the morning dose, and Study Exit/Early Termination and as appropriate at the Follow-up Visit. Day 2 vital signs should be collected approximately 24 hours after the Day 1 dose is administered. Pulse and blood pressure will be measured after 5 minutes supine and again at 1 and 3 minutes after standing for all scheduled time points, with exception of Day 1, Day 2, and Day 16 in cohorts where CSF collection is performed using an indwelling catheter, when only supine measurements will be taken.
- (g) Only for CSF cohorts: A neurological assessment and eye examination (ophthalmological assessment of the retina, fundoscopy) will be performed on Day -2 (baseline collection through single lumbar puncture), Day -1 (baseline collection through indwelling catheter) and Day 15.
- (h) Lumbar spine radiography (for CSF cohorts only) if one has not been performed within the past 12 months prior to the screening visit.
- (i) A standard 12-lead ECG (single) will be recorded at Screening, Check-in, Day 1 (predose [within 60 minutes prior to dosing], and at 1.5 hour postdose (morning dose), Day 16 (predose [within 60 minutes prior to dosing], and at 1 and 2 hours after morning dose, Day 10 (predose), and Study Exit/Early Termination and as appropriate at the Follow-up Visit.

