# 11.1.5.3 Vital Signs

Individual results of vital signs that meet Takeda's markedly abnormal criteria will be summarized and provided in the data listings. Baseline, postdose, and changes from Baseline in vital sign measurements will be summarized. All vital sign data will be provided in the data listings.

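### The only planned orthostatic output leaves out any standing blood-pressure fall, whatever its size, that lacks a heart-rate rise above 20 beats/min

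*SAP*

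**What the plan says.** SAP Appendix C gives one rule for orthostatic hypotension. Its pressure part is "Orthostatic Systolic Blood Pressure < -20 mm Hg OR Orthostatic Diastolic Blood Pressure < -10 mm Hg", held in brackets. Outside the brackets stands "AND Heart Rate Increase > 20 beats/min". The changes are signed: "Orthostatic measurement = standing vital measurement – supine vital measurement".

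SAP Section 8.11.3 says that orthostatic hypotension "will be calculated at every time point where standing and supine measurements are available". The output is a subject mapping: "The mapping of the subjects who meet the criteria for orthostatic hypotension will be listed by study visit as a table". Counts and percentages of subjects are specified in that section for the Appendix B vital-sign criteria. None is specified for orthostatic change.

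The readings come from Protocol Section 3.0, footnote (f): "Pulse and blood pressure will be measured after 5 minutes supine and again at 1 and 3 minutes after standing". Days 1, 2 and 16 are supine only in cohorts with an indwelling catheter.

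Two other statements bear on the point. SAP Section 8.11.3 says "Listings of all vital signs data will be provided in Appendix 16.2", and Protocol Section 11.1.5.3 says "All vital sign data will be provided in the data listings". Neither is limited to subjects who meet Appendix C.

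**The concern.** The rule carries the name of a pressure event, but a pressure fall alone can never satisfy it. The heart-rate condition applies to both the systolic and the diastolic route, and no size of fall overrides it. The rule can therefore label a smaller fall and pass over a larger one. Neither document gives a reason for joining the two conditions.

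Safety and tolerability are the primary objective, and the protocol takes paired supine and standing readings repeatedly. The analysis is descriptive, with 6 active subjects per cohort. What the reader of the report sees by dose therefore depends on what the tables pick out. If standing falls are picked out only when the heart rate also rises by more than 20 beats/min, a dose-related pattern of falls with a smaller rise would have to be found by reading the listings.

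**Working it through.** **Inputs**

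- Appendix C: orthostatic hypotension = (dSBP < -20 or dDBP < -10) and dHR > 20, where d is standing minus supine.
- SAP Appendix B, lower limits: SBP <85, DBP <50, pulse <50. These are absolute values with no heart-rate-rise condition.
- Protocol Section 7.2, criterion 19: supine pressure at entry within 90 to 140 systolic and 50 to 90 diastolic.
- Protocol Section 3.0, footnote (f): predose and 1, 4 and 12 hours after dosing, on Day 1 and Days 3 to 16.
- SAP Section 7.0: 6 active and 2 placebo subjects per cohort.

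The plan states no figure on this point, so there is none to reproduce.

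**Step 1. How much paired data feeds the rule.** Day 1 plus Days 3 to 16 is 15 dosing days, and 15 × 4 = 60 time points on dosing days. Where Days 1 and 16 are supine only, 13 × 4 = 52 remain.

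**Step 2. The rule applied as written.** The values are illustrative, and all supine pressures are within the entry limits.

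| Supine BP, HR | Standing BP, HR | dSBP/dDBP, dHR | Pressure condition | Appendix C | Appendix B on standing values |
|---|---|---|---|---|---|
| 120/75, 65 | 95/70, 90 | -25/-5, +25 | met | met | not met |
| 120/75, 65 | 95/70, 80 | -25/-5, +15 | met | not met | not met |
| 130/80, 65 | 90/55, 75 | -40/-25, +10 | met | not met | not met |
| 140/90, 60 | 85/50, 80 | -55/-40, +20 | met | not met | not met |
| 120/75, 65 | 80/48, 70 | -40/-27, +5 | met | not met | met |

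Rows 1 and 2 have the same pressure fall and differ only in heart rate; one is mapped and the other is not. Rows 3 and 4 have larger falls than row 1 and meet neither appendix. Row 5 is absent from the orthostatic mapping but is tabulated as a markedly abnormal vital sign, provided that standing readings are evaluated.

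**Step 3. Where the gap lies.** If Appendix B covers standing readings, the falls that neither appendix picks out are those that meet the pressure condition, come with a heart-rate rise of 20 or less, and end at SBP ≥85 and DBP ≥50 with no other Appendix B limit crossed. If Appendix B covers supine readings only, it picks out no standing value, and the gap is wider. SAP Section 8.11.3 takes all observations into the Appendix B evaluation but does not mention position.

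**Step 4. What the extra condition can do in a small group (illustration only).** Let p be the assumed share of subjects with a fall meeting the pressure condition, and q the assumed share of those whose fall comes with a rise >20. The chance that at least one of 6 active subjects is picked out is 1 - (1 - p)^6 on pressure alone and 1 - (1 - pq)^6 with both conditions. For p = 0.20 and q = 0.50, pq = 0.10 and 1 - 0.90^6 = 0.469, against 1 - 0.80^6 = 0.738 on pressure alone.

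| p | Pressure alone | q = 0.75 | q = 0.50 | q = 0.25 |
|---|---|---|---|---|
| 0.10 | 0.469 | 0.374 | 0.265 | 0.141 |
| 0.20 | 0.738 | 0.623 | 0.469 | 0.265 |
| 0.30 | 0.882 | 0.783 | 0.623 | 0.374 |

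The documents give neither p nor q. The table shows the direction and a possible range; it does not estimate the loss in this trial.

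**The case against.** The strongest reply is that nothing is hidden. All vital-sign values are listed. Appendix B values are flagged, counted and mapped without any heart-rate-rise condition. Protocol Section 10.1 lets the investigator record any unfavorable finding as an adverse event, and treatment-emergent events are tabulated. This stands. A reader might infer from Appendix C that a fall without a heart-rate rise is never reported, and the documents do not support that.

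A reader might also suppose that a very large fall, say 50 mm Hg systolic with a rise of 15 beats/min, would go unflagged everywhere. That is mostly not so if standing readings are evaluated. From a supine SBP below 135, a fall of 50 ends below 85 and meets Appendix B, and entry allows supine SBP of 90 to 140. The gap is mainly in falls that end at or above 85/50.

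Third, the rule is explicit, prespecified and programmable, and the protocol does not contradict it. The vital-sign primary endpoint runs through Appendix B, and the escalation criteria in Protocol Section 6.2 do not refer to Appendix C. No adverse events of special interest are named. All of this stands too, and it limits the consequence to a descriptive safety display.

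The other routes still do not replace a summary. The listings hold raw values, with no planned flag or count for a standing fall that fails Appendix C. Appendix B looks at levels and does not measure change. Adverse-event recording depends on judgement at the time and is no systematic count by dose.

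**Conclusion.** The point holds in a limited form. A pressure fall of any size without a heart-rate rise above 20 beats/min is not identified as orthostatic hypotension and is absent from the only planned orthostatic output. It is left to the raw listings unless it meets Appendix B or is recorded as an adverse event.

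An added compulsory condition can only lower the number of subjects picked out, so the direction is certain relative to the pressure condition alone. The size is unknown. It is tempting to put a percentage on the falls missed, but the documents give no distribution of orthostatic changes, and any such figure would reflect the inputs chosen.

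No primary-endpoint percentage and no escalation decision rule changes. The conclusion takes no view on which definition of orthostatic hypotension is clinically right. It rests on the wording of Appendix C and Section 8.11.3, and on the SAP's silence about whether Appendix B covers standing readings.

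**What to change.** In SAP Appendix C and Section 8.11.3, keep the present thresholds and the composite. Add a table by dose group and pooled placebo with the number and percentage of subjects who have at least one postdose:

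- (a) SBP change < -20 or DBP change < -10 mm Hg;
- (b) heart-rate increase >20 beats/min;
- (c) both at the same time point, which is the present composite.

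Give the subject mapping for each row. A subject may enter (a) and (b) at different time points without entering (c), so the rows should not be read as adding up.

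The cost is two rows beyond the composite, with counts and percentages for all three, from data already collected. No procedure changes. More subjects will be flagged, including some on placebo; the pooled placebo column gives the context for reading them.
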